Embryo-fetal malformations in rats and rabbits have been observed with losmapimod. Study drug will not be administered to women of childbearing potential unless they are employing adequate contraceptive measures (Section 5.5.1). Pregnancy testing is required before randomization and before dispensation of study drug at all other visits, as specified in the schedule of events (Table 2 and Table 3). Study drug will be discontinued if a female participant becomes pregnant during the treatment period. Unexpected pregnancies will be reported with instructions for appropriate follow-up (Section 6.6).

Drug-Drug Interactions

Losmapimod is considered unlikely to have a clinically relevant drug-drug interaction with substrates or inhibitors of cytochrome P450, P-gp, human organic anion transporting polypeptides (OATP) 1B1 and OATP1B3, human organic anion transporter (OAT) 1, or human renal organic cation transporter (OCT) 2. Losmapimod inhibits multidrug and toxin extrusion (MATE) 1 and MATE2-K renal transporters in vitro with a low risk of clinically relevant interaction. Both losmapimod and its major metabolite, FTX-5508, are in vitro inhibitors of human breast cancer resistance protein (BCRP), and FTX-5508 is a relatively potent in vitro inhibitor of OAT3 (further details are presented in the IB). If possible, avoid co-administration of study drug with MATE 1, BCRP, or OAT3 substrates with a narrow therapeutic index. Careful monitoring for adverse effects of these agents is advised if, in the opinion of the investigator, co-administration is warranted (Section 6.2.1). The inhibition of MATE2-K is not considered a clinical drug-drug interaction risk when comparing potency of in vitro transporter inhibition to projected losmapimod C_{max} values at the 15 mg BID dose.

Infection/Immunity

Based on its pharmacology, losmapimod has a modest but broad inhibitory influence on various inflammatory cytokines. Thus, losmapimod may theoretically have an impact on immunity, and be associated with an increased risk of infection. Incidence of infections to date has been similar in losmapimod versus placebo in controlled studies (further details are presented in the IB). Information for all infections identified as SAEs will be collected (Section 6.2.1.2). Subjects who have received attenuated live vaccines within 6 weeks prior to randomization will be excluded (Section 4.1.2).

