3.1.2. Open-Label Extension

Once subjects reach Week 48, they will have the option to roll over into the OLE, with all subjects receiving 15 mg PO losmapimod tablets BID. Subjects who wish to roll over into the OLE must complete all procedures from the Week 48 end of placebo-controlled treatment period/start of OLE visit (Table 2).

Subjects will remain in the OLE until 90 days after commercial drug is available post regulatory approval or until the study is discontinued by the sponsor. All subjects who complete or discontinue from treatment will complete a safety follow-up visit 7 days (± 3 days) after the last dose of study drug.

During the OLE, subjects will attend clinic visits approximately every 12 weeks (Table 3). Study drug (open-label losmapimod) will be administered BID and should be taken with food.

Blood samples for PK (losmapimod concentration) will be collected after dosing at the Week 144 clinic visit, preferably ≥ 1 hour after dosing.

Safety and tolerability will be evaluated based on the assessment of AEs, AESIs, SAEs, laboratory tests, ECGs, vital signs, and physical examinations.

The full schedule of assessments for the OLE is provided in Table 3. Scheduled visits may be split over 2 days if required, with a maximum of 5 business days in between visits. Unscheduled visits may be performed if clinically indicated.

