9. Standard 12-lead ECG demonstrating QTcF >450 msec for male subjects or QTcF >470 msec for female subjects at screening. If QTcF exceeds 450 msec for males or 470 msec for females, the ECG will be repeated 2 more times, and the average of the 3 QTcF values will be used to determine the subject's eligibility.
10. History of cardiac dysrhythmias requiring anti-arrhythmia treatment(s) or history or evidence of abnormal ECGs that, in the opinion of the investigator or medical monitor, would preclude the subject's participation in the study.
11. Blood donation (of approximately 1 pint [500 mL] or more) or any significant loss of blood within 90 days before the first dose of study drug, as determined by the investigator.
12. Vaccination with a live attenuated vaccine within 6 weeks of randomization and throughout the study.
13. Use of any anticoagulants for at least 1 month and anti-platelet agents for at least 1 week before the baseline biopsy, as they increase the risk of hematomas following skeletal muscle biopsy.
14. Male subjects with a female partner who is planning to become pregnant during the study or within 90 days after the last dose of study drug.
15. Positive pregnancy test or is known to be pregnant or lactating. All female subjects of child-bearing potential must have a negative serum β -human chorionic gonadotropin (β -hCG) pregnancy test at screening and a negative urine pregnancy test prior to randomization.
16. Alcohol, analgesic/opioid, and/or illicit drug abuse, as defined by the American Psychiatric Association Diagnostic and Statistical Manual of Mental Disorders, Fifth Edition (American Psychiatric Association, 2013), in the last 6 months before screening or a positive test for drugs of abuse at screening.
17. Any current mental condition (psychiatric disorder, senility, or dementia) that, in the opinion of the investigator, may affect study compliance or prevent understanding of the aims, investigational procedures, or possible consequences of the study.
18. Use of another investigational product within 30 days or 5 half-lives (whichever is longer), or according to local regulations, or currently participating in a prospective study with an investigational product, whether it concerns an experimental drug or a medical device. Note: concurrent participation in natural history studies (non-drug, non-device studies) may be acceptable if confirmed in writing by the sponsor.

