4.2. WITHDRAWAL OF SUBJECTS FROM STUDY TREATMENT AND/OR THE STUDY

The duration of the placebo-controlled treatment period is defined for each subject as the time between the date the written informed consent was signed through 1) the completion of the Week 48 visit if the subject is rolling over into the OLE or 2) the completion of the safety follow-up visit after the end of treatment if the subject is not rolling over into the OLE. The duration of the OLE is defined for each subject as the time after completion of the Week 48 visit through completion of the safety follow-up visit after the end of treatment or discontinuation of the study.

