5.5.1. Contraception Requirements

Subjects of child-bearing potential must be willing to practice an approved method of birth control for the duration of the study and until 90 days after the last dose of study drug.

A female subject is eligible to participate if she is of non-child-bearing potential, defined as premenopausal females with permanent sterilization (includes hysterectomy, bilateral oophorectomy, or bilateral salpingectomy in a female subject of any age); or postmenopausal, defined as 12 months of spontaneous amenorrhea; or, if of child-bearing potential, if she is using a highly effective method for avoidance of pregnancy and will continue to use these methods for the duration of the study and until 90 days after the last dose of study drug.

Male subjects must agree to use one of the contraception methods listed below for the duration of the study and until 90 days after the last dose of study drug.

The following is the all-inclusive list of the highly effective methods for avoiding pregnancy in females of child-bearing potential (ie, the methods have a failure rate of less than 1% per year when used consistently and correctly and, when applicable, in accordance with the product label) (Hatcher et al, 2007):

- Complete abstinence from penile-vaginal intercourse when this is the preferred and usual lifestyle
- Oral contraceptive, either combined or progestogen alone
- Injectable progestogen
- Implants of etonogestrel or levonorgestrel
- Estrogenic vaginal ring

- Percutaneous contraceptive patches
- Intrauterine device or intrauterine system
- Tubal sterilization
- Essure micro-insert system (provided confirmation of success 3 months after procedure)
- Male partner sterilization (vasectomy with documentation of azoospermia) prior to the female subject's entry into the study, and this male is the sole partner for that subject. The information on the male sterility can come from the site personnel's review of the subject's medical records; medical examination of the subject, and/or semen analysis; or interview with the subject on his medical history. Sterilized males (vasectomy with documentation of azoospermia) must use condoms until 90 days after last dose of study drug.
- Male condom combined with a female diaphragm, either with or without a vaginal spermicidal (foam, gel, film, cream, or suppository). Nonoxynol-9 is the critical component in most spermicides.

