6.6. PREGNANCY

Pregnancy is not regarded as an AE unless there is a suspicion that the study drug may have interfered with the effectiveness of a contraceptive medication. Any pregnancy that occurs during study participation must be reported as an SAE. Study staff should complete the paper Pregnancy Initial Report Form and fax the form to [REDACTED] Pharmacovigilance within 24 hours of awareness or call the [REDACTED] safety hotline to report. To ensure subject safety, irrespective of the treatment received by the subject, any pregnancy occurring during study drug administration or until follow-up must be reported within 24 hours of the investigator's knowledge of the event to the sponsor.

If a woman becomes pregnant while on study drug, the study drug must be discontinued immediately. The investigator must counsel the subject and discuss the potential risks to the pregnancy and the possible effects on the embryo or fetus. The pregnancy must be followed up to determine the outcome (including spontaneous miscarriage, elective termination, normal birth, or congenital abnormality) and status of mother and child, even if the subject was discontinued from the study. Pregnancy complications and elective terminations for medical reasons must be reported as an AE or SAE. Spontaneous miscarriages must be reported as an SAE.

Any SAE occurring in association with a pregnancy that is brought to the investigator's attention after the subject has completed the study and considered by the investigator as possibly related to the study drug must be promptly reported to [REDACTED] and Fulcrum Therapeutics.

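### Pregnancy reporting in Protocol Section 6.6 is not aligned with the 90-day precaution period, so capture of pregnancies conceived after the safety follow-up visit depends on outcome and causality

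*Protocol*

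**What the plan says.** **Reporting.** Protocol Section 6.6 describes the reporting period in two ways. One sentence states: "Any pregnancy that occurs during study participation must be reported as an SAE". A later one states that "any pregnancy occurring during study drug administration or until follow-up must be reported within 24 hours" once the investigator knows of it. The section does not say what *follow-up* means.

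**Last contact.** Section 3.1.2 says that subjects who complete or discontinue treatment "will complete a safety follow-up visit 7 days (± 3 days) after the last dose of study drug". Section 4.2 ends a subject's time in the open-label extension at "completion of the safety follow-up visit after the end of treatment or discontinuation of the study". Routine collection of adverse events (Section 6.2.1.4) and the last scheduled urine pregnancy test (Tables 2 and 3) also end at the safety follow-up visit.

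**Precautions.** Section 5.5.1, on subjects who are able to have children, says that they "must be willing to practice an approved method of birth control for the duration of the study and until 90 days after the last dose", and it sets the same 90 days for male subjects. Inclusion criterion 7 repeats this for both sexes. Exclusion criterion 14 excludes male subjects whose female partner is "planning to become pregnant during the study or within 90 days after the last dose of study drug".

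**Stated background.** Section 1.5 says: "Embryo-fetal malformations in rats and rabbits have been observed with losmapimod". It links this to contraception in women of child-bearing potential.

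**After completion.** Two clauses still apply. Section 6.6 asks for prompt reporting of a serious adverse event associated with a pregnancy if the investigator hears of it and considers it possibly related. Section 6.2.1.4 asks for later serious events that are believed to be related to study drug.

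**The concern.** The protocol sets a precaution period after the last dose and cites malformations in two animal species as background. One would expect it to collect pregnancies over the same period, or to say why it does not. As written, the duty to report seems to stop about a week after the last dose.

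Capture after that point is selective. Whether a pregnancy is recorded depends on how it turns out and on a causality judgement. Uncomplicated pregnancies, and adverse outcomes judged unrelated, would drop out, so any late reports would have no count of pregnancies to set them against. Long-term safety is the primary objective of the open-label extension, so completeness of this information matters even if few cases are expected.

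**Working it through.** The plan states no figure on this point, so there is nothing to reproduce. The check is window arithmetic followed by a comparison of the clauses.

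**Inputs**
- Precaution period after the last dose: 90 days (inclusion 7, exclusion 14, Section 5.5.1).
- Day of the safety follow-up visit, f: 7, with a window of 4 to 10 (Section 3.1.2 and Tables 2 and 3).
- Assumption: *follow-up* in Section 6.6 means this visit. No other post-dose contact is scheduled, and the study-participation wording, read with Section 4.2, leads to the same end.

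**Formulas:** covered share = f/90; uncovered share = (90 − f)/90.

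| f (days) | Covered | Uncovered days | Uncovered share |
|---|---|---|---|
| 4 | 4/90 = 4.4% | 86 | 95.6% |
| 7 | 7/90 = 7.8% | 83 | 92.2% |
| 10 | 10/90 = 11.1% | 80 | 88.9% |

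Most of the 90 days lies after the visit wherever the visit falls in its window.

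**What the clauses require, case by case**
1. *Conceived during dosing or before the safety follow-up visit.* Reportable. Section 6.6 goes by when the pregnancy occurs, so one discovered later is still within its terms.
2. *Conceived after the visit and by day 90, with a serious event that the investigator hears of and considers possibly related.* The event is reportable under Section 6.6, and under Section 6.2.1.4 if it is believed to be related.
3. *Conceived after the visit and by day 90, with no serious event or with one judged unrelated.* No clause requires a report.
4. *Pregnancy in a partner of a male subject.* Section 6.6 does not name it. The instruction to follow a pregnancy to outcome sits in a paragraph about a woman who conceives while taking study drug. A broad reading of the general reporting sentence might include partners, but the text does not settle it.

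The requirement to follow outcome after a subject has been discontinued does not change case 3, because it concerns pregnancies that began on study drug.

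The 4-to-10-day range does not fit everyone. Under Section 4.2.2, a subject who stops drug but stays in the study is covered for longer. A late early-termination visit may also be combined with the safety follow-up, which can move that visit beyond day 10.

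**The case against.** **A reader might infer that the two periods contradict each other.** They do not. One says how long precautions last and the other says what sites must report. A site can obey both.

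**A reader might take day 7 as the stated end of reporting.** It is an inference, because Section 6.6 leaves *follow-up* undefined. It is the likely reading, and the ambiguity is itself worth removing.

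**A reader might treat all 90 days as fetal exposure.** No passage says so. Section 1.3 gives half-lives of about 10 hours for losmapimod and 12 hours for the metabolite. At the earliest follow-up, day 4 (96 hours), that is 96/10 = 9.6 and 96/12 = 8 half-lives. Simple decay then leaves about 0.1% and 0.4%. This does not show what the precaution period should be, and the documents do not use it to justify a shorter reporting period. It does mean that the percentages above measure calendar time and not risk.

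**A reader might infer that nothing is collected after the visit, or that the trial cannot describe the risk behind its criteria.** Neither follows. Pregnancies that begin on drug must be reported throughout. SAP Table 4-1 schedules visits to Week 216 (Day 1512), and 80 to 86 days is 5.3% to 5.7% of that span. A congenital anomaly is a serious adverse event by definition (Section 6.2.1.2), so it stays reportable through the conditional route. With 80 subjects of both sexes enrolled, no reporting window would give a useful estimate of malformation risk.

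**The reason for the male rules is not documented.** Section 1.5 ties the animal findings to women of child-bearing potential only. It would be a guess to say that they explain exclusion criterion 14.

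**Some material is not visible.** The consent pages were removed and the pregnancy report form is not shown. Either could ask subjects to notify the site of a later pregnancy.

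These points reduce the weight of the concern. None of them supplies a duty to report an uncomplicated pregnancy conceived after the safety follow-up visit and within the 90 days.

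**Conclusion.** The point holds as a limited gap in safety data. If *follow-up* means the safety follow-up visit held within its window, 80 to 86 of the 90 precaution days have no general duty to report. Capture in those days depends on a serious event, on the investigator's awareness and on a judgement of relatedness. Whether partner pregnancies are reportable is left open.

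The documents do not support calling this a contradiction, a complete absence of late reporting, or a failure of the trial to address reproductive risk. No efficacy endpoint, sample size or error rate is affected. The conclusion rests on the day-7 reading and on the visible text only. It takes no position on how long either period should be.

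**What to change.** Amend Section 6.6 so that it:
- reconciles the reporting period with the precaution period in Sections 4.1.1, 4.1.2 and 5.5.1, or states why the two differ;
- defines *follow-up*;
- states whether pregnancies in partners of male subjects are reportable and followed to outcome.

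At the existing safety follow-up visit, have sites tell subjects to notify them of a pregnancy that begins later within the reconciled period. If the consent form or the pregnancy report form already says this, a cross-reference is enough.

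The change concerns data collection only. It adds no visit or test and alters no treatment or contraception rule. The cost is protocol wording, one instruction at the last visit, and a small amount of reporting after last contact. That reporting would rely on subjects coming forward, so capture would improve but would not be guaranteed.

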6.7. SAMPLE COLLECTIONS

Processing, storage, and shipping procedures for all clinical laboratory, PK, and target engagement samples are provided in a laboratory manual.

7. STATISTICAL AND ANALYTICAL PLAN

Details regarding the statistical methods and definitions will be provided in statistical analysis plan(s) (SAP[s]). Separate SAPs will be prepared for each treatment period of the study. The SAP for the placebo-controlled treatment period will be finalized prior to database lock/freeze for the IA.

Any deviations from the SAP(s) are to be justified in the clinical study reports. Statistical analyses will be performed using Version 9.3 or higher of SAS (SAS Institute, Cary, NC).

Analyses will be generated separately for the placebo-controlled treatment period and the OLE.

7.1. PLACEBO-CONTROLLED TREATMENT PERIOD

7.1.1. Primary Endpoint

The primary endpoint of the placebo-controlled treatment period is the change from baseline in DUX4 activity in affected skeletal muscle at Week 16 or Week 36, as measured by QRT-PCR in a panel of DUX4-regulated gene transcripts.

7.1.2. Secondary Endpoints

The secondary endpoints of the placebo-controlled treatment period are as follows:

- Safety and tolerability of losmapimod as defined by the following:
 - Type, frequency, severity, seriousness, and relationship of AEs to losmapimod
 - Incidence of AESIs
 - Number of subjects who prematurely discontinue study drug due to an AE
 - Frequency of clinically significant changes in laboratory test, ECG, vital sign, and physical examination results
- Change from baseline in MFF, LMV, and MFI at Week 12, Week 24 (if applicable) and Week 48
- Plasma concentrations of losmapimod at Week 4, Week 12, Week 16, Week 24, Week 36, and Week 48
- Concentrations of losmapimod in skeletal muscle biopsy at steady state at Week 16 or Week 36
- Target engagement parameters in blood, and skeletal muscle biopsy at Week 16 or Week 36

7.1.3. Exploratory Endpoints

The exploratory endpoints of the placebo-controlled treatment period are as follows:

- Change from baseline in COAs, including
 - RWS with and without weights at Week 4, Week 12, Week 24, and Week 36

- Classic and FSHD TUG at Week 4, Week 12, Week 24, and Week 36
- Muscle strength by hand-held quantitative dynamometry at Week 4, Week 12, Week 24, Week 36, and Week 48
- MFM Domain 1 at Week 12, Week 24, Week 36, and Week 48
- FSHD-HI at Week 4, Week 12, Week 24, Week 36, and Week 48
- PGIC at Week 4, Week 12, Week 16, Week 24, Week 36, and Week 48
- Change from baseline in inflammatory, immune, apoptotic, and other muscle disease transcripts may be conducted in muscle biopsy at Week 16 or Week 36 and in circulating proteins in plasma and serum at Week 4, Week 12, Week 16, Week 24, Week 36, and Week 48.

7.2. OPEN-LABEL EXTENSION

7.2.1. Primary Endpoint

The primary endpoint of the OLE is the safety and tolerability of long-term treatment of losmapimod based on AEs, clinical laboratory tests, ECGs, vital signs, and physical examination.

7.2.2. Secondary Endpoint

The secondary endpoint of the OLE is the plasma concentrations of losmapimod after long-term dosing (at every-12-week time points).

7.3. SAMPLE SIZE CALCULATIONS

Assuming an effect size of 0.70, a sample size of 68 subjects (34 subjects per group) will be needed to provide 80% power with a 2-sided test at a 0.05 significance level to detect a difference between losmapimod and placebo in change from baseline in DUX4 activity in affected skeletal muscle after 16 or 36 weeks (depending upon when the muscle biopsy was performed) during the placebo-controlled treatment period. Assuming that approximately 10% of subjects will be non-evaluable, approximately 76 subjects will be randomly assigned at a 1:1 ratio to losmapimod and placebo (38 subjects per group).

7.4. ANALYSIS SETS

The following analysis sets will be used in the statistical analyses.

Full analysis set (FAS): The FAS will consist of all subjects who are randomly assigned to receive double-blind study drug in the placebo-controlled treatment period. All analyses using the FAS will group subjects according to randomized treatment. The FAS is the main analysis population for key study endpoints (Section 7.6.1). For the secondary and exploratory endpoints, subjects who already transitioned into the OLE portion under protocol version 3.0 will be analyzed as randomized, in this analysis population.

Per-protocol set (PPS): The PPS will consist of all FAS subjects who fulfill all inclusion/exclusion criteria and do not have any significant protocol deviations. All analyses using the PPS will group subjects according to randomized treatment. PPS analyses will be conducted for key study endpoints (Section 7.6.1) to assess robustness of key study inferences.

Safety analysis set: The safety analysis set will consist of all subjects who receive any study drug. All analyses using the safety analysis set will group subjects according to treatment actually received.

Pharmacokinetic analysis set: The PK analysis set will consist of all subjects who receive at least 1 dose of losmapimod and have evaluable PK data for losmapimod.

Pharmacodynamic analysis set: The PD analysis set will consist of all subjects who receive at least 1 dose of losmapimod and have evaluable PD data for losmapimod.

Open-label losmapimod (Pre-COVID-19) analysis set: This analysis set will consist of subjects who were already transitioned into open-label losmapimod under version 3.0 of the protocol. This analysis set will be used for sensitivity analysis, to assess secondary/exploratory endpoints in this subset of subjects.

Open-label analysis set: The open-label analysis set will consist of all subjects who complete 24 weeks of treatment in the placebo-controlled treatment period and receive at least 1 dose of open-label losmapimod in the OLE. Safety and efficacy analyses in the OLE will be based on this analysis set.

